A total of 162 CBCT scans of mandibular permanent premolars and molars belonging to Egyptian individuals are selected according to the following:

Inclusion criteria:

- First and second mandibular permanent premolars and molars of Egyptian patients starting from 18 years, males or females.
- Intact roots without fractures or cracks.
- Posterior teeth are present and their adjacent and opposing teeth.
- Absence of radiological evidence of dental malocclusion that could have altered the position of premolars or molars.
- CBCT scans of mandibular first and second premolars and molars using 20 x 10 cm FOV, 0.4mm voxel resolution.

Exclusion criteria:

- Evidence of apicectomy or periapical surgery.
- Odontogenic or non-odontogenic pathology.
- Congenital deformity of the mandible.
- External Root resorption.
- Previous history of fracture of the mandible.
- Tomographic images of poor quality or artifacts interfering with the detection of mandibular canal and apical morphology of the teeth.

Variables:

1. The crowding and overlapping of the mandibular posterior teeth .
2. Extraction of the adjacent or the opposing tooth may cause tilting of the tooth or over eruption of the opposing tooth.
3. Attrition of the teeth may cause over eruption of the teeth.
4. The presence of dental anomalies may influence the position of the tooth to the inferior alveolar canal.

Data Sources / Measurements:

Retrospective Data Analysis will be performed after the CBCT images are pooled from the computer database by convenient sampling technique.

CBCT images will be obtained from patients who required CBCT examination as part of their dental examination, diagnosis or treatment planning without exposing them to unnecessary radiation dose for the research purpose.

All the CBCT examinations are scanned by Planmeca Promax 3D®, 20 x 10 cm FOV, 0.4 mm voxel resolution, 90 kVp, 8 mA and 13.5 seconds exposure time.

To assess the shortest distance from the root apices to the border of the inferior alveolar canal, the multiplanar reconstruction view of the manufacturer's software viewer (Planmeca Romexis) with its axial, sagittal and coronal plane will be used, and the cross-sectional images through the mandible will be also used.

Cross sectional images will be oriented parallel to the long axis of the tooth, then the shortest distance from the deepest point of root apices and superior border of the inferior alveolar canal will be obtained to be examined (**Umut et al 2017**).

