CBCT images will be interpreted by two oral radiologists independently; blinded from demographic data of the patients and from the results of each other.

All measurements will be assessed, once by the first investigator and then another time two weeks later for intra-observer reliability. The second investigator will assess the measurements once for inter-observer reliability.

Then inter-observational and intra-observational variability between the observers will be evaluated.

Bias:

No source of bias.

Study Size:

The aim of the study is to assess the relationship between the roots of mandibular premolars and molars and the superior border of inferior alveolar canal in Egyptian population. Based on the previous paper by **San Chong,et al,2017**,the prevalence of alveolar nerve 78%.Using a precision of 5, a design effect set at 1 with 95%CI(confidence interval), a total sample size of 162 will be sufficient. The sample size was calculated by Epi info.

Sampling Strategy: The sample will be collected by convenient sampling technique.

Statistical Methods:

Data will be analyzed using IBM SPSS advanced statistics (Statistical Package for Social Sciences), version 24 (SPSS Inc., Chicago, IL). Numerical data will be described as mean and standard deviation or median and range. Categorical data will be described as numbers and percentages. Comparisons between males and females for normally distributed numeric variables will be done using Student's t-test while for non-normally distributed numeric variables will be done by Mann-Whitney test. Comparisons between categorical variables will be performed using the chi square test. A p-value less than or equal to 0.05 will be considered statistically significant. All tests will be tailed.

References

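### The male/female comparison uses pooled-variance Student's t or Mann-Whitney by normality; if the sexes differ in both number and SD, Student's t misses its 5% level, and Welch's t avoids this at almost no cost

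*Protocol*

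**What the plan says.** The Statistical Methods section of the protocol fixes the test by the shape of each variable: "Comparisons between males and females for normally distributed numeric variables will be done using" Student's t-test, while the comparison "for non-normally distributed numeric variables will be done by Mann-Whitney test". It names no normality test or cut-off and no unequal-variance form of the t-test. The threshold is given as "A p-value less than or equal to 0.05 will be considered statistically significant". The sentence on sidedness, "All tests will be tailed", has lost the number of tails.

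On who is compared, the inclusion criteria admit "First and second mandibular permanent premolars and molars of Egyptian patients starting from 18 years, males or females", with no quota or target by sex. Sampling Strategy says "The sample will be collected by convenient sampling technique". Study Size says that "a total sample size of 162 will be sufficient"; that number rests on a single proportion and not on a sex comparison. No SD of the distance is given for either sex.

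The primary outcome is a distance in mm, and the research question asks which roots lie closest to the canal. The male/female comparison appears only in Statistical Methods.

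**The concern.** Student's t estimates one common variance. When the groups are unequal in size and also in spread, the pooled standard error is wrong. It is too small if the smaller group is the more variable one, and too large in the reverse case. Since nothing fixes the number of men and women, an uneven split is quite possible, and the plan has no protection if the SDs differ as well. Reported sex differences could then be somewhat too easy or too hard to declare.

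The second issue is interpretation. Mann-Whitney does not test a mean difference in mm. If normality verdicts differ between roots, the table of sex comparisons would mix two questions, and a reader looking down the column could not compare one root with another.

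**Working it through.** **Inputs.** From the protocol: N = 162 scans, threshold 0.05, Student's t or Mann-Whitney by normality, no sex split, no SD by sex. Assumed: two-sided tests; splits from 81:81 to 120:42 with either sex the smaller; SD ratios of 1, 1.25 and 1.5.

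**The plan's own figure.** The protocol gives no error rate or power for the sex comparison, so there is nothing of that kind to reproduce. Its 162 is used here only as the total. It does not follow from the stated inputs (1.96² × 0.78 × 0.22 / 0.05² = 263.7, so 264), but that is a separate matter.

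**Step 1: size of Student's t by formula.** Let s be the smaller group and l the larger.

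- True variance of the mean difference: V = σs²/ns + σl²/nl
- Variance the pooled test uses, on average: P = sp² × (1/ns + 1/nl), with sp² = [(ns − 1)σs² + (nl − 1)σl²] / 160
- k = √(V/P); actual size ≈ 2 × Pr(t160 > 1.975/k)

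Example: 108:54, SD 1.5 in the smaller group and 1 in the larger.

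- V = 2.25/54 + 1/108 = 0.05093
- sp² = (53 × 2.25 + 107 × 1)/160 = 1.4141
- P = 1.4141 × 0.02778 = 0.03928
- k = √(0.05093/0.03928) = 1.139; 1.975/1.139 = 1.734; size ≈ 8.5%

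With the larger SD in the larger group: V = 0.03935, P = 0.05100, k = 0.878, 1.975/0.878 = 2.248, size ≈ 2.6%.

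**Step 2: the same by simulation.** Normal data, equal means, 10,000 to 40,000 datasets per cell.

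| Split | SD ratio | Larger SD in smaller group: formula / simulated | Larger SD in larger group: formula / simulated |
|---|---|---|---|
| 81:81 | 1.5 | 5.0% / 5.1% | same (equal groups) |
| 97:65 | 1.25 | 6.1% / 6.1% | 4.1% / 4.2% |
| 97:65 | 1.5 | 6.9% / 7.0% | 3.5% / 3.7% |
| 108:54 | 1.5 | 8.5% / 8.7% | 2.6% / 2.6% |
| 113:49 | 1.5 | 9.3% / 9.8% | 2.3% / 2.1% |
| 120:42 | 1.5 | 10.4% / 10.5% | 1.8% / 1.8% |

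With equal SDs, k = 1 at any split and the size is 5%; the simulated values are 4.7% to 5.2%.

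**Step 3: Welch's t.** It stayed between 4.5% and 5.5% in all 30 scenarios of one simulation set (five splits, three SD ratios, normal and moderately skewed gamma data with shape 4).

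**Step 4: the normality switch.** The rule was simulated as Shapiro-Wilk at 5% in each sex, which is an assumption because the protocol names no test. With equal SDs the two-stage rule kept 4.5% to 5.5% at every split, so the switch alone does not break the level. With truly normal data it still went to Mann-Whitney in about 9% to 10% of runs (expected 1 − 0.95² = 9.75%). Two roots with the same kind of distribution can therefore land on different tests by chance.

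**Step 5: cost of Welch.** With equal SDs and a true difference of 0.5 SD, simulated power was 84.5% for Welch against 84.7% for Student at 108:54, and 78.3% against 78.9% at 120:42.

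**The case against.** Choosing between Student's t and Mann-Whitney by distribution is a conventional rule, and it holds about 5% when the SDs are equal, whatever the split. The failure needs two conditions together, unequal numbers and unequal SDs, and the protocol shows neither. The upper figures need a split of 2:1 or worse and an SD ratio of 1.5, which is a lot for one anatomical distance in men and women. At 97:65 with a ratio of 1.2, a simulation gives only 5.7% or 4.3%. The pooled form is inferred from the name of the test. Which row of the SPSS output is read could be left to an analysis plan, and the sex comparison is not the research question. All of this stands, and it limits the weight of the point. It does not remove it: the protocol names a specific test, and a safer one is available at almost no loss.

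Three stronger readings do not hold. A reader might infer that convenience sampling itself inflates the error rate. It affects representativeness; here it matters only because the split is left open. A reader might infer that the planned tests do break the 5% level, or that roots will be tested on different quantities. The documents support only that both may happen. Finally, a reader might treat rejections by Mann-Whitney in skewed data with equal means and unequal SDs as false positives of that test. Those are two different distributions, so its null hypothesis is not true there. The rejection rate also depends heavily on the assumed skewness, about which the protocol says nothing.

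**Conclusion.** The point holds conditionally. For N = 162, assumed splits from 97:65 to 120:42 and assumed SD ratios of 1.25 to 1.5, the two-sided type I error of pooled Student's t runs from about 2% to about 10%, depending on which sex is the smaller and the more variable. Welch's t stays near 5%. With equal SDs or an 81:81 split there is no problem with the level of Student's t. Independently of this, the variable-by-variable choice of test may leave roots with results on different scales. The weight is minor: this is a secondary comparison, and the ranking of roots by distance is unaffected.

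**What to change.** In Statistical Methods, replace Student's t-test with Welch's t-test (the SPSS row 'equal variances not assumed'). Name it in advance for the male/female comparison at every root, whatever the normality result, and report the mean difference in mm with its 95% CI. Mann-Whitney may be reported alongside as a sensitivity check.

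The cost is about one sentence of text. The planned software already prints the row. The loss of power if the SDs are in fact equal is a few tenths of a percentage point (0.2 at 108:54 and 0.6 at 120:42 in the check above). No change to sampling or to the number of scans per sex is needed.

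### The male-female comparison of apex-to-canal distance is fixed without age, so in this convenience sample a sex difference could not be separated from any age difference between the men and women scanned

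*Protocol*

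**What the plan says.** The Statistical Methods section of the protocol fixes the comparison: "Comparisons between males and females for normally distributed numeric variables will be done using" Student's t-test, and the Mann-Whitney test is named for those that are not normal. No covariate is named. A chi-square test is given for categorical variables, but the primary outcome is a distance in millimetres. The sex comparison is therefore the only test named for that kind of outcome.

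Other sections bear on how it can be read:

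- **Inclusion criteria:** "Egyptian patients starting from 18 years, males or females". No upper age limit is set.
- **Sampling Strategy:** "The sample will be collected by convenient sampling technique". No matching or stratification by age or sex is described.
- **Data Sources / Measurements:** the two readers are "blinded from demographic data of the patients", which implies that such data are held.
- **Variables:** among influences on tooth position, "Attrition of the teeth may cause over eruption of the teeth". Age is not named.
- **Bias:** the whole entry is "No source of bias".

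The aim, the outcome table and the research question concern the distance itself and which roots lie nearest the canal. None of them mentions sex.

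**The concern.** A two-sample test of men against women compares everything that differs between the two groups, not sex alone. Patients were scanned for their own clinical reasons and picked by convenience, so nothing in the design makes the age mix of men and women alike. With adults of any age eligible, there is room for a gap. If distance also changes with age, the crude difference mixes the two effects, and the chance of p at or below 0.05 with no sex effect at a given age rises above 5%.

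What is at stake is how a secondary result is read. A difference declared significant could be reported as a feature of male and female anatomy when part or all of it reflects who happened to be scanned. The Bias entry rules this out in advance, which an unadjusted comparison in a convenience sample cannot justify.

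**Working it through.** The protocol gives no figure for this comparison, so there is none to reproduce. It states no SD of distance, sex split, age distribution or age effect. Everything below except N = 162 and the 0.05 level is an assumption. Two-sided testing is also assumed, because the sentence on sidedness lacks a word.

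**Inputs**
- N = 162 and significance at p ≤ 0.05: Study Size and Statistical Methods.
- 81 men and 81 women, SD 2 mm: assumed.
- Age effect 0 to 0.4 mm per decade, mean age gap 0 to 10 years: assumed.

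**Step 1: bias of the crude difference.** Bias = age slope × age gap.
- Slope 0 or gap 0: 0 mm.
- 0.2 mm per decade × 0.5 decade = 0.1 mm.
- 0.2 × 1 decade, or 0.4 × 0.5 decade = 0.2 mm.
- 0.4 × 1 decade = 0.4 mm.

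**Step 2: standard error.** SE = 2 × √(1/81 + 1/81) = 2 × 0.157 = 0.314 mm. The 95% half-width is 1.96 × 0.314 = 0.62 mm.

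**Step 3: false-positive rate.** With s = bias/SE, the probability of rejecting when there is no sex effect is Φ(s − 1.96) + Φ(−s − 1.96).

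| Bias (mm) | s | Rejection rate |
|---|---|---|
| 0 | 0 | 5.0% |
| 0.1 | 0.32 | 6.2% |
| 0.2 | 0.64 | 9.8% |
| 0.4 | 1.27 | 24.7% |

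**Step 4: the same check without assuming an SD in mm.** Let ρ be the within-sex correlation of age with distance and g the age gap in SDs of age. The bias is then about ρ × g SDs of distance.

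| ρ | g | Bias (SD) | Rejection rate |
|---|---|---|---|
| 0 | any | 0 | 5.0% |
| 0.1 | 0.2 | 0.02 | 5.2% |
| 0.2 | 0.5 | 0.10 | 9.8% |
| 0.3 | 0.5 | 0.15 | 15.9% |

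The two scales agree where they meet: 0.10 SD is 0.2 mm at SD 2 mm, and both give 9.8%. A 60:102 split changes little (15.2% in place of 15.9% in the last row). The 24.7% figure corresponds to a bias of 0.4/2 = 0.20 SD. At g = 0.5 that needs ρ = 0.20/0.5 = 0.4, stronger than any correlation in this table, so it is an extreme corner.

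**Step 5: cost of adjusting.** Residual degrees of freedom go from 162 − 2 = 160 to 159. With equal groups, the variance of the sex coefficient is multiplied by about 1 + g²/4. At g = 0.5 this is 1.0625, so the standard error rises by about 3%, before any gain from age explaining variance. At g = 0 there is no such rise.

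**The case against.** The strongest reply is that the study does not ask about sex. A crude male-female contrast is legitimate description in a cross-sectional anatomical study and misleads only if read as an effect of sex independent of age, a reading the protocol never proposes. Adjusting a secondary comparison is also often left to the SAP, which is not shown. The protocol lists other influences on tooth position, so choosing age alone is partly the reviewer's judgement.

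Much of this stands. The crude comparison is valid as description, and the point is secondary. The SAP argument has less force, because the protocol is not silent here: it names the tests, and neither can take age into account. Age is a reasonable first covariate because the age rule for entry already requires it to be known, at least to the extent of applying the limit.

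Two stronger readings may tempt a reader:

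- **That any sex difference found would be an age artefact or beyond interpretation.** The documents do not support this. Confounding needs both an age gap between the sexes and an age effect on distance. The protocol shows neither, and if either is absent the bias is zero.
- **That the protocol itself names an ageing mechanism.** It says only that attrition may lead to over-eruption. It mentions neither age nor time, and that item does not mention distance to the canal. The link from age through wear to distance is plausible, but it is an inference.

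**Conclusion.** A minor limitation of a secondary analysis, worth correcting because the correction is cheap. As fixed, the sex comparison cannot distinguish a sex difference in distance from an age difference between the men and women sampled, and the Bias entry is too strong. The false-positive rate lies between 5% (no bias) and about 25% (steepest assumed slope with the widest assumed gap). The correlation-scale range reaches about 16%. These figures rest on the assumed age effect, age gap and sex split, and the millimetre figures also on the assumed SD. They show possible size and are not estimates for this sample. The aim and the research question are unaffected.

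**What to change.** In Statistical Methods, state that age will be tabulated by sex. For each root, report the male-female difference in mm with a 95% CI from a linear model with sex and age as a continuous variable. Keep the crude t-test or Mann-Whitney comparison alongside as a descriptive result. In the Bias section, replace "No source of bias" with a statement that scans are a convenience sample, that the age mix of men and women is not controlled by design, and that sex differences should be read with this in mind.

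The cost is a few sentences, about one degree of freedom in 160 and slightly more analysis work. No new data should be needed, provided that the age used to apply the entry rule is kept in the analysis file.
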